2.5. MRI protocol and analysis

Our hospital has a standardised magnetic resonance imaging (MRI) protocol for non-traumatic OHCAs. MRI imaging includes diffusion weighted image (DWI), and apparent diffusion coefficient (ADC) map. The MRI was obtained between 72–96 h after ROSC. Forty contiguous DWI sections per patient were acquired using a 3T scanner (Achieva 3 T; Philips Medical System, The Netherlands). The standard of b=1000 s/mm² was used for all DWIs. ADC maps were created from the mono-exponential calculation of DWI with a commercial software and workstation system (Leonardo MR Workplace; Siemens Medical Solutions, Erlangen, Germany). For quantitative analysis of ADC to evaluate the effect of lumbar CSF drainage on attenuation of brain swelling, images were processed and analysed using software (FMRIB Software Library, Release 5.0 (c) 2012, The University of Oxford) that can extract brain tissue by eliminating cranium, optic structure, and extra-cranial soft tissues. Images were retrieved in Digital Imaging and Communications in Medicine format from picture archiving and communication system servers at the hospital and were converted to NITFI format using MRIcron (http://www.nitrc.org/projects/mricron). ADC thresholds ranged from 0 to 1590 X 10⁻⁶ mm²/s to exclude artefacts or pure CSF [16]. The percentage of voxels (PV) meant number of voxels below different ADC thresholds was divided by total number of voxel.

The % voxels of ADC values (PV)

$$PV = \frac{Voxel \text{ numbers of ADC value}}{Voxel \text{ numbers of ADC value}} \frac{ADC \text{ threshold}}{0}$$

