The Effect of Lumbar CSF drainage on the Neurologic Outcome Improvement

in OHCA underwent TTM

1. Introduction

Global cerebral ischaemic-reperfusion brain injury following cardiac arrest (CA) can lead to intracranial hypertension and, occasionally, acute brain swelling [1,2]. Even small increases in brain volume due to oedema can result in harmful increases in intracranial pressure due to the brain's rigid encasement. The previous studies demonstrated a higher intracranial pressure (ICP) was strongly associated with and seemed predictive of a poor outcome, and higher ICP following global cerebral ischaemia immediately after ROSC, and severe blood-brain barrier (BBB) disruption began at 24 h after ROSC in the poor neurologic outcome group treated with target temperature management (TTM) [3, 4].

Several therapeutic approaches have been established for the treatment of increased ICP in traumatic brain injury, including TTM, elevation of the head, sedation, volume resuscitation, maintenance of adequate arterial oxygenation, cerebrospinal fluid drainage via a ventriculostomy, moderate hyperventilation, and mannitol administration [5]. However, despite these various therapies, a considerable number of patients remain nonresponsive to aggressive management strategies. During the last decades, controlled lumbar cerebrospinal fluid (CSF) drainage has been considered to be contraindicated in the setting of increased ICP because of the possibility of transtentorial or tonsillar herniation [6–8]. In contrast, a recent report on the use of lumbar CSF drainage to treat refractory increased ICP suggested that this controversial therapeutic strategy might be efficient and a valuable treatment when applied to carefully selected patients had discernible basal cisterns and controlled release of CSF under monitoring of ICP and vital signs [9, 10]. Plus, much of the CSF volume is present in the subarachnoid spaces and cisterns around the brain. This CSF is not accessible for drainage by ventriculostomies but is accessible by lumbar drainage [11].

However, to the best of our knowledge, there is no study on the effect of lumbar CSF drainage to improve neurologic outcome in CA patients treated with TTM. We aimed to evaluate the effect of lumbar CSF drainage on neurologic outcome in post-CA patients treated with TTM.

2. Methods

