2.1. Study design and patients

This was a prospective single-centre study conducted from November 2019 to October 2021 on patients who had been treated with TTM following CA. The primary endpoint was to evaluate the effect of the lumbar CSF drainage on attenuation of brain swelling and improvement of the neurologic outcome in post-CA patients treated with TTM. The data were collected from the electrical medical record. We named the patients were treated with our standard protocol as the non-lumbar CSF drainage group, whereas the patients treated with the protocol and the lumbar CSF drainage were called as the lumbar CSF drainage group. The neurologic status of the patients was obtained on the 6-month follow-up after return of spontaneous circulation (ROSC). Neurological outcome was assessed using the Glasgow-Pittsburgh cerebral performance categories (CPC) scale. The good outcome group was defined as a CPC 1 or 2, and the poor outcome group as a CPC between 3 and 5. Resuscitated cardiac arrest patients whose Glasgow coma scale (GCS) was 8 or less after the return of spontaneous circulation (ROSC), and who underwent TTM were included in the study. The exclusion criteria for this study were as follows: (1) \leq 18 y of age, (2) traumatic CA or interrupted TTM (due to haemodynamic instability), (3) not eligible for TTM (i.e., intracranial haemorrhage, active bleeding, known terminal illness, or poor pre-arrest neurological status), (4) ineligible for LP (i.e., brain computed tomography showed severe cerebral oedema, obliteration of the basal cisterns, occult intracranial mass lesion, or coagulopathy: platelet count $< 40 \times 10^3$ /mL or international normalized ratio (INR) > 1.5),¹² (5) on extracorporeal membrane oxygenation, (6) unable to consent to LP, and (7) refusal of further treatment by the next of kin.

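### The only swelling variable, the share of voxels below an ADC threshold, reflects restricted diffusion and not brain volume, so a lower share alone cannot be read as less swelling

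*Combined protocol and SAP*

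**What the plan says.** All references are to the combined protocol and SAP.

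- **Objective.** Section 2.1 sets the primary endpoint as being to "evaluate the effect of the lumbar CSF drainage on attenuation of brain swelling and improvement of the neurologic outcome". It names no variable, time point or direction for the swelling part.
- **Measure.** Section 2.5 describes the image processing under the purpose "For quantitative analysis of ADC to evaluate the effect of lumbar CSF drainage on attenuation of brain swelling". The summary is PV: "number of voxels below different ADC thresholds was divided by total number of voxel". The prose gives no threshold value. ADC values are kept between 0 and 1590 × 10⁻⁶ mm²/s "to exclude artefacts or pure CSF".
- **Timing.** "The MRI was obtained between 72–96 h after ROSC". No earlier MRI is described.
- **Rationale.** The Introduction states the harm in terms of volume: "Even small increases in brain volume due to oedema can result in harmful increases in intracranial pressure". It also reports that "severe blood-brain barrier (BBB) disruption began at 24 h after ROSC in the poor neurologic outcome group".
- **Other candidates.** ICP is monitored through the catheter (2.4), but the data list (2.3) holds only the value immediately after ROSC, which 2.7 uses for matching. CT oedema appears only as an exclusion (2.1). The model named in 2.7 is for neurologic outcome, and no analysis of PV is named there.

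**The concern.** The rationale is about brain volume inside a rigid skull, but the variable is a ratio of voxel counts. A voxel counts toward PV when its ADC is low, which is a sign of restricted diffusion. Free water lies at the other end of the scale, as the plan's own upper cut for CSF shows. Water that leaks through a damaged barrier adds volume and raises ADC, so for that component PV falls while the brain swells. For restricted diffusion, PV rises with injury.

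PV therefore has no fixed direction with swelling. Since it is the only variable tied to that part of the primary endpoint, a group difference in PV could stand as a swelling result when it shows something else, or even the opposite.

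**Working it through.** **The plan's own figure.** The only calculated figure is the sample size in 2.6, based on ICP at 24 h. Difference 18.57 − 13.22 = 5.35; pooled SD = √[(3.99² + 5.61²)/2] = 4.868; n per group = 2 × (1.960 + 2.326)² × (4.868/5.35)² = 30.4, so 31 per group and 62 in total, assuming equal groups. It reproduces, does not involve PV, and is unaffected by this point.

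**Direction of PV.** The documents give no voxel values, so every input below is an assumption chosen for illustration (ADC in 10⁻⁶ mm²/s).

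*Model A.* 30% of voxels are injured (mean 550, SD 80) and 70% normal (800, SD 100); the threshold is 650. Added water of fraction w and ADC F, between 2000 and 3000, shifts each mean to (mean + wF)/(1 + w) and divides each SD by 1 + w.

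- No added water: 0.30 × Φ(1.25) + 0.70 × Φ(−1.50) = 0.30 × 0.894 + 0.70 × 0.067 = 31.5%.
- w = 0.05, F = 2000: means 619.0 and 857.1, SDs 76.2 and 95.2; PV = 0.30 × 0.658 + 0.70 × 0.0148 = 20.8%.
- w = 0.05, F = 3000: means 666.7 and 904.8; PV = 0.30 × 0.413 + 0.70 × 0.0037 = 12.7%.
- w = 0.03: 25.1% (F = 2000) and 20.3% (F = 3000).

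With cellular injury unchanged, the 5% gain lowers PV by 31.5 − 20.8 = 10.7 to 31.5 − 12.7 = 18.8 points. With no added water, the same PVs would need an injured share of (0.208 − 0.067)/(0.894 − 0.067) = 17% or (0.127 − 0.067)/(0.894 − 0.067) = 7% instead of 30%.

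*Sensitivity of the size, w = 0.05 unless stated:*

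| Change to Model A | PV without water | PV with water |
|---|---|---|
| Water in uninjured voxels only | 31.5% | 27.1–27.9% |
| Threshold 450 | 3.2% | 0.1–0.4% |
| Threshold 550 | 15.4% | 1.9–5.5% |
| Threshold 1200 | about 100% | about 100% |
| Injured share 50% instead of 30% after water, w = 0.03 | 31.5% (30% injured) | 33–40% |

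In the last row PV rises, so it shows the worsening correctly. With w = 0.05 the same 50% share gives 0.5 × 0.413 + 0.5 × 0.0037 = 20.9% (F = 3000) to 0.5 × 0.658 + 0.5 × 0.0148 = 33.6% (F = 2000), so even the sign is then open.

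*Model B, simulated voxels.* Tissue mean 850, SD 150; 15% of voxels lowered by 350; PV counted among voxels above 0 and up to 1590.

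| Threshold | Uninjured | Injury only | Injury plus global ADC rise of 50 / 100 / 200 / 300 |
|---|---|---|---|
| 450 | 0.4% | 6.0% | 4.0 / 2.4 / 0.7 / 0.15% |
| 650 | 9.1% | 20.4% | 15.3 / 11.5 / 6.0 / 2.4% |

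Restricted diffusion raises PV. A global ADC rise lowers it at every threshold tried from 400 to 1000.

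*Exception.* If 15% or 30% of voxels are drawn, non-lesion voxels only, and raised by 900, most leave the 1590 window. At threshold 450, PV then goes up from 6.0% to 6.6% or 7.5% because the denominator shrinks.

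**The case against.** The strongest reply has four parts.

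1. **The plan states no direction for PV.** A reader might infer from 2.1 and 2.5 that a lower PV will be scored as less swelling. That is the natural reading, but no sentence says it, so there is no rule to delete. This stands. What is missing is a statement of what a PV difference may be taken to mean.

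2. **PV is not wrong for all oedema.** A reader might infer that PV falls whenever the brain takes up water. The documents do not support that: they do not link oedema type to ADC, and the sign argument rests on general MR physics plus the plan's treatment of CSF as high ADC. PV can track restricted diffusion correctly, and voxels passing 1590 can raise it. This stands and limits the point to extracellular water in voxels that stay inside the window.

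3. **The size is assumed.** The 11 to 19 points need water in every voxel, fixed injury and a threshold of 650. Section 2.5 speaks of different thresholds, not low ones. Nor do the documents give a reason to expect more extracellular water with drainage; if drainage reduced it, PV would rise and the error would count against the intervention. This stands.

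4. **Barrier disruption is reported for poor-outcome patients only**, without an amount. This stands: it makes the component plausible at 72 to 96 h but does not show that it dominates.

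None of this turns PV into a measure of swelling. It removes any claim about the size or likely direction of the error in this trial.

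**Conclusion.** The point holds in a limited form. PV is the only variable that the plan ties to swelling. It contains no volume, and two processes that can both accompany swelling move it in opposite directions. A lower PV alone therefore cannot be read as less swelling.

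No single size can be given. Under the assumptions shown, a 5% water gain lowers PV by anything from almost nothing to about 19 points, depending on the threshold and on where the water goes. It would be too strong to say that the plan will report worse swelling as improvement, or that PV is uninformative: PV remains usable for diffusion restriction. The 6-month neurologic outcome and the sample size of 62 are not affected. The change should be made because it alters what the trial may conclude on part of its primary endpoint.

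**What to change.** 1. In 2.1 and 2.5, describe PV as a measure of diffusion restriction (cytotoxic injury), state that a lower PV alone is not evidence of attenuated swelling, and limit the PV-based conclusion to diffusion restriction.
2. In 2.5, also report from the same ADC maps the share of voxels above the normal tissue range, with that range written into the plan. Count brain-mask voxels above 1590 separately, so that they do not leave the denominator unseen.
3. A ratio of brain to intracranial volume from the same scan may be added as exploratory. It should not be the condition for a swelling claim: there is no baseline MRI, drainage itself may alter the CSF spaces, and a count cut at 1590 would drop the wettest voxels.

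The cost is a few sentences and one more count on images already acquired. The downside is that the swelling part of the primary endpoint becomes a narrower claim.

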2.6. Sample size

A previous study reported ICP on 24 h after ROSC was 13.22 ± 3.99 mmHg in good outcome and 18.57 ± 5.61 mmHg in poor outcome [17], 62 patients were needed to achieve the power of 0.99 at a significance level of 0.05 (two-sided test).

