2.3. Data collection

The following data were collected from the database: age, sex, presence of a witness at the time of the collapse, bystander cardiopulmonary resuscitation (CPR), first monitored rhythm, aetiology of cardiac arrest, time from collapse to CPR (no flow time), time from CPR to ROSC (low flow time), sequential organ failure assessment (SOF) score, ICP measured on immediate after ROSC, time from ROSC to inserting a lumbar drainage catheter placed through the lumbar vertebral interspace into the subarachnoid space (ICP time), , and CPC at 6 months after ROSC.

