2.7. Statistical analysis

NCT number: not yet assigned

We reported continuous variables as median with interquartile range or as mean and standard deviation depending on the normal distribution. Categorical variables were reported as frequencies and percentages. We performed the propensity score matching with age, sex, presence of a witness at the time of the collapse, bystander CPR, first monitored rhythm, causes of CA, no flow time, low flow time, sequential organ failure assessment (SOFA) score, and ICP on immediate after ROSC between both groups. Comparisons between the two groups were made using the chi-square test, Fisher's exact test, the Mann-Whitney U test, or two-tailed *t*-test. Multivariate logistic regression models were built to identify the effect of the lumbar CSF drainage on the neurologic outcome at 6 months after ROSC. The estimated odds ratio was considered to assess risk. All statistical analyses were performed using the PASW/SPSSTM software, version 18 (IBM Inc., Chicago, USA). Results were considered significant at P < 0.05.

Conflict of interest statement: The authors have no conflict of interest to report

Acknowledgements: This work was supported by the National Research Foundation Korea (NRF) grant funded by the Korea government (MSIT) (No. 2019R1F1A1041024).

References

2. Polderman KH. Mechanisms of action, physiological effects, and complications of hypothermia. Crit Care Med 2009;37:S186–202.

6. Cushing H. Some aspects of the pathological physiology of intracranial tumors. *Boston Med Surg J* 1909; 141:71–80.

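### The 0.99 power for 62 patients belongs to a prognostic contrast in 24 h ICP, not to drainage versus no drainage on MRI swelling or 6-month CPC

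*Combined protocol and SAP*

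**What the plan says.** Section 2.6 rests on one published contrast: "ICP on 24 h after ROSC was 13.22 ± 3.99 mmHg in good outcome and 18.57 ± 5.61 mmHg in poor outcome". From it the plan concludes that "62 patients were needed to achieve the power of 0.99 at a significance level of 0.05 (two-sided test". It does not say how the 62 patients divide between groups, or whether 62 is counted before or after propensity matching.

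The trial's own question is in section 2.1: "The primary endpoint was to evaluate the effect of the lumbar CSF drainage on attenuation of brain swelling and improvement of the neurologic outcome". The groups there are the standard protocol with and without lumbar drainage. Neurologic outcome is CPC 1–2 against CPC 3–5 at 6 months.

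Section 2.5 assigns brain swelling to MRI at 72–96 h, through "quantitative analysis of ADC to evaluate the effect of lumbar CSF drainage on attenuation of brain swelling". Section 2.7 assigns the clinical outcome to regression: "Multivariate logistic regression models were built to identify the effect of the lumbar CSF drainage on the neurologic outcome at 6 months after ROSC".

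ICP appears by name in two lists. Section 2.3 has "ICP measured on immediate after ROSC", and the matching set in section 2.7 ends with "sequential organ failure assessment (SOFA) score, and ICP on immediate after ROSC between both groups". Neither list names ICP at 24 h.

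**The concern.** Good and poor outcome are the two levels of this trial's outcome. They are not its treatment groups. A difference in ICP between them shows how well ICP separates patients by prognosis; it says nothing about how far drainage shifts ICP, the MRI measure or CPC. The plan states no drainage effect on any of the three.

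The 0.99 is the only justification offered for the sample size. Read at face value, it suggests that the drainage comparison is almost certain to detect a true effect. If the real power for CPC is well below that, a non-significant result could be mistaken for evidence that drainage does not work.

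**Working it through.** **Step 1. Reproduce the plan's figure.** Inputs from section 2.6: means 13.22 and 18.57 mmHg, SDs 3.99 and 5.61, two-sided α = 0.05, power 0.99. Equal groups are an assumption.

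- Difference: 18.57 − 13.22 = 5.35.
- Pooled SD: √[(3.99² + 5.61²)/2] = 4.868.
- Standardised difference: 5.35/4.868 = 1.099.
- Normal formula: n per group = 2 × [(1.960 + 2.326)/1.099]² = 30.4, rounded up to 31, so 62 in total.
- Noncentral t power: 0.989 at 31 per group, 0.991 at 32.

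The plan's 62 and 0.99 reproduce, which identifies the contrast that was powered.

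**Step 2. Compare that contrast with the trial.**

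| | Sample size (2.6) | Trial (2.1, 2.5, 2.7) |
|---|---|---|
| Groups | Good vs poor outcome, previous study | Drainage vs no drainage |
| Variable | ICP at 24 h | MRI ADC at 72–96 h; CPC 1–2 at 6 months |
| Effect | 5.35 mmHg | None stated |

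No row agrees.

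**Step 3. What 62 patients could give for CPC (illustration).** The documents give no control rate, target gain or allocation. Assumptions: 31 per group, no loss to matching, an unadjusted test, two-sided 0.05. Power is the sum, over all possible 2×2 tables, of the binomial probability of each table that the test rejects. The chi-square is uncorrected.

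| Control rate of CPC 1–2 | Power, +20 points: chi-square | Power, +20 points: Fisher | Rise for 80% power: chi-square | Rise for 80% power: Fisher |
|---|---|---|---|---|
| 10% | 0.516 | 0.391 | 29.5 | 32.8 |
| 20% | 0.408 | 0.313 | 33.5 | 36.7 |
| 30% | 0.372 | 0.278 | 34.2 | 37.3 |
| 40% | 0.371 | 0.278 | 34.1 | 37.0 |
| 50% | 0.372 | 0.278 | 32.8 | 35.2 |
| 60% | 0.408 | 0.313 | 29.7 | 31.9 |
| 70% | 0.516 | 0.391 | – | – |

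Rises are in percentage points, accurate to about 0.1. With an assumed split of 40 and 22, in either direction, power for the 20-point rise over the same control rates is 0.320–0.524 (chi-square) or 0.254–0.461 (Fisher).

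**Step 4. Numbers needed for CPC (illustration).** The normal approximation is n per group = [1.960√(2p̄(1 − p̄)) + 0.842√(p₀(1 − p₀) + p₁(1 − p₁))]²/(p₁ − p₀)², where p̄ is the mean of p₀ and p₁. For 80% power at 20% vs 40% it gives 82 per group (164 in total). At 40% vs 60% it gives 97 per group (194 in total).

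**Step 5. MRI measure.** The documents give no expected difference or SD by drainage group, so its power cannot be computed. For a continuous measure with 31 per group, t-test power at assumed standardised differences of 0.4, 0.5, 0.8 and 1.1 is 0.34, 0.49, 0.87 and 0.989. Power near 0.99 would therefore need a drainage effect of about 1.1 SD.

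**The case against.** The best defence is that 24 h ICP is an implicit surrogate. The Introduction reports that "a higher intracranial pressure (ICP) was strongly associated with and seemed predictive of a poor outcome", and section 2.4 uses drainage to control ICP around a threshold of 15 mmHg, which lies between the two means in section 2.6. The authors may have supposed that drainage moves ICP from the poor-outcome level to the good-outcome level. This is plausible, but no section says so. It would require drainage to close the whole 5.35 mmHg gap, and the result would be power for ICP, still not for CPC or MRI.

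Silence about 24 h ICP is also weak evidence that it would go unanalysed. The data list in section 2.3 omits the MRI variables too, although section 2.5 plainly plans them, and section 2.7 lists generic two-group tests without naming variables. That objection stands, so the finding does not rest on the silence. It rests on the mismatch between section 2.6 and the primary endpoint.

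It is also true that section 2.6 discloses the source of its contrast, that nothing in the plan says a null CPC result would be read as no effect, and that every CPC power above depends on assumed rates and an unadjusted test. The illustrations show how low power could be, not what this trial's power is. Finally, the plan dates conduct from November 2019 to October 2021. If enrolment is complete, the number of patients cannot change and the remedy is disclosure. That limits what can be repaired, but does not make the 0.99 correct.

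**Conclusion.** The concern holds, and the statement must be corrected. The calculation is arithmetically sound, but it answers a question the trial does not ask. The sole power figure in the plan applies to neither half of the primary endpoint. This conclusion needs no outside assumption; it follows from setting section 2.6 beside sections 2.1, 2.5 and 2.7.

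The size of the gap does depend on assumptions. Under those in step 3, a 20-point CPC gain has roughly one-quarter to one-half power, against the stated 0.99, and 80% power needs a gain of about 30 to 37 points from control rates of 10–60%. Loss of unmatched patients would reduce the number analysed. That loss, the power of the adjusted logistic model and the power for the MRI measure cannot be computed from the documents.

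**What to change.** In section 2.6, withdraw 0.99 as the power for the primary endpoint. State how 62 divides between groups and whether it is before or after matching. The sponsor should supply the expected CPC 1–2 rate without drainage, the gain of interest, and the expected difference and SD of the MRI measure, and restate power from these. If they are not available, this text would serve:

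> The figure of 62 was derived from the difference in 24 h ICP between good- and poor-outcome patients of a previous study. It is not the power for the comparison of drainage with no drainage. As an unadjusted approximation on assumed rates (31 per group, before any loss to propensity matching, two-sided 0.05), 62 patients give 37–52% power by chi-square, or 28–39% by Fisher's exact test, for a 20-point rise in CPC 1–2 at control rates of 10–70%. No power is reported for the MRI measure.

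In section 2.7, add:

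> The drainage effects on CPC 1–2 and on the MRI measure are reported with 95% confidence intervals. A non-significant CPC result is not read as evidence of no effect.

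The cost is wording in two sections. No extra patients are needed for the correction itself, but it does not make 62 adequate. The power statement becomes much less favourable, and the MRI half stays without one until the sponsor provides inputs.
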